Table 15.3.1.8.3	Incidence of Related Serious TEAEs by BMI Subgroup	Safety	The number and percentage of subjects reporting related serious TEAEs will be summarized by PT nested within SOC. Percentage will be based on SS. Data of centers 104 and 120 will be excluded.
Table 15.3.1.8.4	Incidence of Related Serious TEAEs by Blood Pressure Subgroup	Safety	The number and percentage of subjects reporting related serious TEAEs will be summarized by PT nested within SOC. Percentage will be based on SS. Data of centers 104 and 120 will be excluded.
Table 15.3.1.8.5	Incidence of Related Serious TEAEs by Race Subgroup	Safety	The number and percentage of subjects reporting related serious TEAEs will be summarized by PT nested within SOC. Percentage will be based on SS. Data of centers 104 and 120 will be excluded.
Table 15.3.1.8.6	Incidence of Related Serious TEAEs by Ethnicity Subgroup	Safety	The number and percentage of subjects reporting related serious TEAEs will be summarized by PT nested within SOC. Percentage will be based on SS. Data of centers 104 and 120 will be excluded.

Listings

No.	Name	Analysis set	Comments
Listing 16.2.3.1	Adverse Event: General	Enrolled	All AEs information will be listed.
Listing 16.2.3.2	Adverse Event: MedDRA Coding	Enrolled	All AEs will be listed by preferred term nested within system organ class.
Listing 16.2.3.3	Serious Adverse Event	Enrolled	All SAEs information will be listed.
Listing 16.2.3.4	TEAEs Leading to Trial Termination	Enrolled	All TEAEs Leading to Trial Termination information will be listed.
Listing 16.2.3.5	TEAEs of Special Interest	Enrolled	All TEAEs of Special Interest information will be listed.

5.6.2 Vital Signs

Vital signs include blood pressure, pulse, height, body weight and BMI data.

Summary statistics for parameter values and absolute parameter change values from Baseline to Visit 6/EDV will be provided for each visit as described in Sections 4.1 and 4.6.

Blood pressure and pulse

Blood pressure and pulse data include:

- Time of first/second/third measurement
- Pulse (bpm)
- Systolic blood pressure (mmHg)
- Diastolic blood pressure (mmHg)

Blood pressure and pulse will be measured in a sitting position at all visits from V1a to V6/EDV, after the subject has rested for at least five minutes.

Median value from the 1st, 2nd and 3rd measurements for systolic, diastolic blood pressure and pulse rate will be summarized in analysis tables. All values from the 1st, 2nd and 3rd measurements for systolic, diastolic blood pressure and pulse rate will be provided in a listing.

Height, body weight and body mass index

Height, body weight and body mass index data include:

- Weight (kg)
- Height (cm)
- Body mass index (kg/m²)

At V1a, height will be measured in all subjects. At V1b to V6 height only has to be determined in adolescent subjects. Body weight will be measured at all visits from V1a to V6/EDV, lightly dressed and without shoes. The determined body weight has to be calculated as BMI. The BMI as a measure for the physical constitution of a ≥18-year-old subject is defined as follows:

$$BMI \text{ at Visit } X \text{ (kg/m}^2\text{)} = \frac{Body \text{ weight at Visit } X \text{ (kg)}}{(Body \text{ height at Visit } 1a \text{ (cm)/100})^2}.$$

The BMI as a measure for the physical constitution of a <18-year-old subject is defined as follows:

$$BMI \text{ at Visit } X \text{ (kg/m}^2\text{)} = \frac{Body \text{ weight at Visit } X \text{ (kg)}}{(Body \text{ height at Visit } X \text{ (cm)/100})^2}.$$

Summary of vital signs will be repeated for defined subgroups.

Tables

No.	Name	Analysis set	Comments
Table 15.3.2.1.1	Summary of Vital Signs	Safety	Vital signs parameters will be summarized descriptively including change from baseline at each visit where assessments were made. Data of centers 104 and 120 will be excluded.
Table 15.3.2.1.2	Summary of Vital Signs by Weight Subgroup	Safety	Vital signs parameters will be summarized descriptively by weight subgroup including change from baseline at each visit where assessments were made. Data of centers 104 and 120 will be excluded.
Table 15.3.2.1.3	Summary of Vital Signs by BMI Subgroup	Safety	Vital signs parameters will be summarized descriptively by BMI subgroup including change from baseline at each visit where assessments were made. Data of centers 104 and 120 will be excluded.
Table 15.3.2.1.4	Summary of Vital Signs by Blood Pressure Subgroup	Safety	Vital signs parameters will be summarized descriptively by blood pressure subgroup including change from baseline at each visit where assessments were made. Data of centers 104 and 120 will be excluded.
Table 15.3.2.1.5	Summary of Vital Signs by Race Subgroup	Safety	Vital signs parameters will be summarized descriptively by race subgroup including change from baseline at each visit where assessments were made. Data of centers 104 and 120 will be excluded.
Table 15.3.2.1.6	Summary of Vital Signs by Ethnicity Subgroup	Safety	Vital signs parameters will be summarized descriptively by ethnicity subgroup including change from baseline at each visit where assessments were made. Data of centers 104 and 120 will be excluded.

Listings

No.	Name	Analysis set	Comments
Listing 16.2.4.1	Vital Signs (EN)	Enrolled	All vital signs records will be listed.

5.6.3 Clinical Laboratory Evaluation

Clinical laboratory values are collected as described in Section 1. The following parameters are collected:

Hematology: hemoglobin, red blood cell count, mean corpuscular volume (MCV) and associated parameters, hematocrit, MCH, white blood cell count, differential white blood cell count including neutrophils, lymphocytes, eosinophils, basophils and monocytes, platelet count.

Biochemistry: sodium, potassium, chloride, creatinine, blood urea nitrogen (BUN), calcium, glucose, total proteins, albumin, total cholesterol (HDL, LDL cholesterol), triglycerides, gamma glutamyl transferase, total and direct bilirubin, alkaline phosphatase (ALP), alanine aminotransferase (ALAT), aspartate aminotransferase (ASAT), creatine phosphokinase (CPK), lactate dehydrogenase (LDH).

Pregnancy tests: serum β-hCG and urine dipstick tests.

Urinalysis (dipstick test): leukocytes, nitrite, protein, glucose, ketones, blood, pH, urobilinogen, bilirubin, hemoglobin.

All laboratory test results are assigned an LNH classification according to whether the value is lower than (L), within (N) or higher than (H) the reference range for that parameter as provided by the corresponding laboratory. Clinical significance of laboratory values is evaluated by the investigator.

According to CRF investigator will evaluate only total cholesterol (not separate cholesterol fractions) deviation as clinically significant or not.

If both absolute and percent values of eosinophils, basophils, monocytes or neutrophils will be out of range then clinical significance evaluation will be assigned for absolute value of respective parameter.

Laboratory parameters will be summarized by calculating summary statistics on the absolute values and on the change from baseline V4 and V6/EDV (hematology and urinalysis variables) and from baseline to V3, V4, V5 and V6/EDV (biochemistry variables). The number and percent of subjects with values outside the limits of reference range will be summarized. Shift tables will be provided to illustrate changes with respect to the laboratory normal ranges between V1a and V4 and V6/EDV (hematology variables) and between V1a and V3, V4, V5 and V6/EDV (biochemistry variables).

Tables

No.	Name	Analysis set	Comments
Table 15.3.3.1.1	Summary of Clinical Laboratory Tests: Hematology	Safety	Default summary statistics of absolute and absolute change results at V1a, V4 and V6/EDV will be presented. Data of centers 104 and 120 will be excluded.
Table 15.3.3.1.2	Summary of Clinical Laboratory Tests: Biochemistry	Safety	Default summary statistics of absolute and absolute change results at V1a, V3, V4, V5 and V6/EDV will be presented. Data of centers 104 and 120 will be excluded.
Table 15.3.3.1.3	Summary of Clinical Laboratory Tests: Urinalysis dipstick	Safety	Number and percentage of subjects for each parameter based on the number of subjects with non-missing data at will be presented. Data of centers 104 and 120 will be excluded.
Table 15.3.3.1.4	Clinical Laboratory Tests: Incidence of Hematology Abnormalities	Safety	Number and percentage of subjects for each parameter will be presented in normal, abnormal NCS and abnormal CS categories at specified visit. Percentage will be based on the number of subjects with non-missing data. Data of centers 104 and 120 will be excluded.
Table 15.3.3.1.5	Clinical Laboratory Tests: Incidence of Biochemistry Abnormalities	Safety	Number and percentage of subjects for each parameter will be presented in normal, abnormal NCS and abnormal CS categories at specified visit. Percentage will be based on the number of subjects with non-missing data. Data of centers 104 and 120 will be excluded.

Table 15.3.3.1.6	Clinical Laboratory Tests: Shift Table of Hematology Results	Safety	Number and percentage showing changes in the number and frequency of subjects with respect to the normal range between Visit 1a and V4, V6/EDV will be presented. Subjects with missing data will be presented as part of a “missing” category. Percentage will be based on SS. Data of centers 104 and 120 will be excluded.
Table 15.3.3.1.7	Clinical Laboratory Tests: Shift Table of Biochemistry Results	Safety	Number and percentage showing changes in the number and frequency of subjects with respect to the normal range between Visit 1a and V2, V3, V4, V5 and V6/EDV will be presented. Subjects with missing data will be presented as part of a “missing” category. Percentage will be based on SS. Data of centers 104 and 120 will be excluded.

Listings

No.	Name	Analysis set	Comments
Listing 16.2.5.1	Laboratory Data: Hematology	Enrolled	Values of laboratory tests will be listed.
Listing 16.2.5.2	Laboratory Data: Biochemistry	Enrolled	Values of laboratory tests will be listed. Pregnancy test results will be listed in the separate listing.
Listing 16.2.5.3	Laboratory Data: Urinalysis	Enrolled	Urinalysis dipstick data will be listed. Pregnancy test results will be listed in the separate listing.
Listing 16.2.5.4	Laboratory Data: Pregnancy tests	Enrolled	Pregnancy test serum β-hCG and urine dipstick tests results will be listed.

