A population pharmacokinetic (PK) analysis planned in the whole subject population, will obtain sparse blood samples to determine plasma concentrations of LF111 at Visits 2 and 4. In total, four blood samples will be collected: two samples each will be collected during the 1st cycle (Visit 2: Cycle 1, Week 3, Day 20±2) and during the 6th cycle (Visit 4: Cycle 6, Week 3, Day 20±2) of treatment.

Number of subjects (planned):

Screened (enrolled): Approximately 1500. Screening will continue until a sufficient number of subjects have been allocated to treatment.

Allocated to treatment: At least 995 non-breastfeeding subjects, including a minimum of 75 subjects > 35 years.

Note: Breastfeeding women are also allowed to be enrolled in the trial.

Collected medication cycles: At least 5000 evaluable cycles (cycles with intercourse without back-up contraceptive at least once per month based on electronic diary question 'Did you have sexual intercourse since the beginning of the cycle?') for non-breastfeeding subjects aged ≤ 35 years (at the time of trial enrollment).

At least 200 women having completed 13 cycles of treatment will be analyzed for safety.

Diagnosis and main criteria for inclusion:

1. Sexually active, postmenarcheal and premenopausal female subjects at risk of pregnancy including breastfeeding women with no upper age limit.
2. Female subjects at risk of pregnancy, between the ages of 15 and 17 (inclusive) provided that
 - Applicable national, state and local laws allow subjects in this age group to consent/assent to receive contraceptive services, and
 - All applicable laws and regulations regarding the informed consent/assent of the subjects to participate in clinical trials are observed.
3. Regular cycles during the last six months before consent/assent when not using hormonal contraception.
4. At least three complete menstrual cycles after delivery (only applicable for women who were pregnant within the last six months and for non-breastfeeding women).
Breastfeeding women can be included six weeks after delivery irrespective of menstrual cycles post-delivery.
5. At screening, maximum systolic blood pressure (median value of three values) ≤ 159 mm Hg and diastolic blood pressure (median value of three values) ≤ 99 mm Hg.
6. Be able and willing to provide written informed consent or assent if the subject is adolescent, prior to undergoing any trial-related procedure.
7. Willing to use trial contraception for thirteen 28-day cycles.

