Duration of treatment for the individual subject: 13 sequential cycles of 28 days

Test product, dose and mode of administration:

LF111 coated tablets (4.0 mg drospirenone), oral administration

Reference therapy, dose and mode of administration: Not applicable.

Criteria for evaluation:

Efficacy:

Primary:

- Pearl index (PI) from evaluable cycles in non-breastfeeding women aged ≤ 35 years (at the time of trial enrollment)

Secondary:

- Pearl Index based on overall cycles (overall PI) in women aged ≤ 35 years (at the time of trial enrollment)
- PI for method failures in women aged ≤ 35 years (at the time of trial enrollment)
- Pregnancy ratio in women aged ≤ 35 years (at the time of trial enrollment)
- Overall PI, PI for method failures, PI (using evaluable cycles) and pregnancy ratio (life table analysis) in all women
- Overall PI, PI for method failures, PI (using evaluable cycles) and pregnancy ratio (life table analysis) in women aged > 35 years

Data from breastfeeding women will be excluded from the efficacy analyses but included in the analyses regarding safety and tolerability.

Safety/Tolerability:

- Adverse events (AEs)

- Vital signs
- Clinical laboratory parameters
- Vaginal bleeding pattern
- IMP acceptability

Pharmacokinetics:

- DRSP plasma concentrations
- Area under the curve (AUC)
- Volume of distribution
- Apparent clearance

Statistical methods:**Statistical analysis:**

Analysis of the primary efficacy variable defined as PI based on evaluable cycles in non-breastfeeding women aged ≤ 35 years (at the time of trial enrollment) will be performed for the Full Analysis Set (FAS). Two-sided 95% confidence interval (CI) for the PI will be calculated assuming that events of pregnancy have a Poisson distribution.

Secondary efficacy analysis will be based on the FAS. Two-sided 95% CIs will be calculated for the overall PI and the method failures PI.

Life table analysis: The pregnancy rate at each cycle and the cumulative pregnancy rate will be calculated (95% CI).

Analysis of safety endpoints will be conducted using the Safety Set only.

All adverse events (AEs) and treatment-emergent AEs (TEAEs) will be summarized by calculating the number and percent of subjects with AEs by preferred term and system organ class. Also TEAEs will be summarized by severity and relationship to treatment. Number and percent of TEAEs leading to trial termination will be provided.

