Laboratory parameters will be summarized by calculating summary statistics on the absolute values and on the change from V1a to V3, V4, V5 and V6. Shift tables will be provided to illustrate changes with respect to the laboratory normal ranges between V1a and V6 (or EDV). The number and percent of subjects with values outside the limits of clinical significance will be summarized.

Analysis of tolerability will be based on FAS.

Number and percent of subjects with bleeding and spotting, scheduled bleeding, scheduled spotting, unscheduled bleeding and unscheduled spotting will be presented for each cycle. The Clopper-Pearson 95% confidence interval for rate of subjects will be calculated. Cumulative rate of subjects for reference periods (summary of cycles 2-4, 5-7, 8-10 and 11-13) will be provided. Cumulative rates only for reference periods will also be presented for number and percent of subjects with prolonged bleeding and spotting $>$ nine days/ $>$ 14 days and the number of bleeding and spotting episodes.

Number and percent of days per cycle and reference period with bleeding and spotting, scheduled bleeding, scheduled spotting and unscheduled bleeding, unscheduled spotting and duration of scheduled bleeding, scheduled spotting, unscheduled bleeding and unscheduled spotting will be analyzed descriptively.

IMP acceptability will be summarized by default frequency tabulation. Shift tables will be provided to illustrate change from V3 to V6/EDV. Additionally for subjects who switched from another oral contraceptive to the IMP default frequency tables will be summarized to present change of subject wellbeing.

Pharmacokinetics analyses of LF111 will be conducted using a population pharmacokinetic method to determine individual estimates of LF111 pharmacokinetic parameters. In addition, a model-based covariate analysis will be performed to explore the effect of pre-defined covariates, including body weight/body mass index, on the apparent clearance of DRSP, and the influence of any significant covariates on the exposure over the dose interval assessed.

Sample size calculation:

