2.6 Sample Size

At least 920 subjects will be allocated to treatment to have at least 5000 evaluable cycles for the PI calculation in non-breastfeeding women aged ≤ 35 years (at the time of trial enrollment). Additionally, a minimum of 75 subjects aged > 35 years will be allocated to treatment. The calculations are based on empirical values including firstly a rate of 24.8% of subjects using back-up contraception or not having intercourse. Secondly, 45% of subjects are assumed to drop out of the trial. The prime target is to collect at least 5000 evaluable cycles.

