5.4 Exposure to IMP and Compliance

5.4.1 Exposure to IMP

Exposure data include:

- Date of the first IMP intake (subject's diary)
- Date of the last IMP intake
- Date of IMP dispensation
- Number of white tablets dispensed
- Number of green tablets dispensed
- Date of IMP collection
- Number of white tablets collected
- Number of green tablets collected
- Numbers of tablets taken (subject's diary)
- Date of IMP intake with time in hours and minutes (subject's diary)

Exposure data are derived from appropriate eCRF pages and diary. If the 1st regular IMP intake (variable PILDT in subject's diary) was not entered, but the first IMP intake (variable BPILDTC in subject's diary) was entered then the 1st regular IMP intake will be derived from BPILDTC by adding time "T00:00".

Derived variables:

Overall treatment duration will be calculated as follows:

Overall treatment duration

$$= \text{Date of the last IMP intake} - \text{Date of the first IMP intake} + 1.$$

Cumulative exposure will be categorized as:

- ≥ 28 days
- ≥ 84 days
- ≥ 168 days
- ≥ 252 days

Missing Entries of IMP Intake in Treatment Diary

Missing IMP intake entries will be classified as total number of missing entries and consecutive missing entries per respective cycle. Total and consecutive number of missing entries will be categorized as:

- Total missing entries over up to 13 cycles
 - 0-2 missing entries
 - 3-5 missing entries
 - 6-8 missing entries
 - 9 or more missing entries
- Total missing entries per separate cycle
 - 0 missing entries
 - 1 missing entries
 - 2 missing entries
 - 3 missing entries
 - 4 or more missing entries
- Active tablet free interval. Active tablet free interval is >48h tablet free interval during the second IMP intake till day 24 of each cycle or >144h interval between the last IMP intake and the first IMP intake in consecutive cycles. Tablet free interval calculation will not take into account cycle days 25-28.

Tables

No.	Name	Analysis set	Comments
Table 15.1.17.1.1	Exposure to Investigational Medicinal Product	Safety	Default summary statistics for the overall treatment duration in days will be presented. Default frequency tabulation for cumulative overall treatment duration will be displayed. Percentage will be based on the number of subjects in the SS. Data of centers 104 and 120 will be excluded.

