5.6.5.2 Transvaginal Ultrasound Examination

Transvaginal ultrasound examinations will be performed at V1a and V6/EDV. The transvaginal ultrasound examination data will be described by the following data:

- Date of ultrasound
- The reason why transvaginal ultrasound was not performed
- Uterus (normal, abnormal, not done)
- Endometrium (normal, abnormal, not done)
- Ovaries (normal, abnormal, not done)
- Were any follicles or cysts identified during the ultrasound procedure (yes, no)
- Diameter of largest follicle (Right ovary)
- Diameter of largest cyst (Right ovary)
- Diameter of largest follicle (Left ovary)
- Diameter of largest cyst (Left ovary)

Transvaginal ultrasound examination abnormal values are assessed as clinically significant or not clinically significant.

Tables

No.	Name	Analysis set	Comments
Table 15.3.6.1.1	Transvaginal Ultrasound Examination	Safety	Number and percentage at each visit will be presented. Percentage will be based on the number of subjects with non-missing data. Data of centers 104 and 120 will be excluded.
Table 15.3.6.1.2	Shift Table for Transvaginal Ultrasound Examination	Safety	Number and percentage showing changes in the number and frequency of subjects with respect to the normal test between baseline and EDV, V6 and V6/EDV will be presented. Subjects with missing data will be presented as part of a "missing" category. Percentage will be based on SS. Data of centers 104 and 120 will be excluded.

Listings

No.	Name	Analysis set	Comments
Listing 16.2.7.2	Transvaginal Ultrasound Examination	Enrolled	Transvaginal Ultrasound examination results will be listed.

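### Laboratory change is summarised at a pooled V6/EDV in SAP 5.6.3, although the protocol synopsis and SAP 2.2.3 specify V6, so values from early stoppers enter the cycle-13 mean

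*SAP*

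**What the plan says.** **Laboratory change.** The protocol synopsis (statistical methods) sets the summary "on the change from V1a to V3, V4, V5 and V6", and SAP 2.2.3 repeats this. In both places EDV appears only in the next sentence, for the shift tables. SAP 5.6.3 instead runs the change summary "from baseline to V3, V4, V5 and V6/EDV (biochemistry variables"), with hematology at V4 and V6/EDV. The comments on Tables 15.3.3.1.1 and 15.3.3.1.2 also end at V6/EDV.

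**Visit handling.** SAP 4.4 gives V6 and EDV one visit number (60) and one label. SAP 4.7 analyses by nominal visit without windowing. Note 1 to the schedule in SAP section 1 has women who stop early undergo the V6 assessments.

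**Vital signs.** SAP 5.6.2: "Summary statistics for parameter values and absolute parameter change values from Baseline to Visit 6/EDV will be provided for each visit". Here SAP 2.2.3 also ends at V6/EDV.

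**Where the SAP does split.** The ultrasound shift table shows changes "between baseline and EDV, V6 and V6/EDV will be presented" (5.6.5.2). The shift tables for dysmenorrhea, mastodynia/mastalgia and cytology do the same.

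**Exposure.** The protocol states: "At least 200 women having completed 13 cycles of treatment will be analyzed for safety". Treatment lasts "13 sequential cycles of 28 days". In SAP 5.4.1, Table 15.1.17.1.1 has cumulative categories of at least 28, 84, 168 and 252 days, and also: "Default summary statistics for the overall treatment duration in days will be presented".

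**The concern.** The last laboratory column is the one a reader will take as the change after 13 cycles. As specified in 5.6.3, it combines women at the end of cycle 13 with women who left at any earlier point, including the first cycles. Two distortions follow, and they can act in opposite directions. An effect that builds with exposure is diluted by short exposures. Women who stopped because of an abnormal value are averaged in and can push the mean the other way. A single pooled mean cannot separate the two.

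This matters most where no later unmixed visit exists. It also touches potassium, because hyperkalemia is an adverse event of special interest (SAP 5.6.1). Separately, the protocol's target of 200 women with 13 cycles cannot be read from an exposure table whose top category is nine cycles.

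**Working it through.** **1. The texts side by side**

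| Summary | Protocol synopsis | SAP 2.2.3 | SAP 5.6 | Consistent? |
|---|---|---|---|---|
| Laboratory change | V6 | V6 | V6/EDV | No |
| Laboratory shift | V6 or EDV | V6/EDV | V6/EDV | Yes |
| Vital-sign change | no rule given | V6/EDV | V6/EDV | Yes |

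The contradiction is therefore confined to the laboratory change summaries.

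**2. Last visit not mixed with early stoppers**

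Note 10 to the schedule limits V3 and V5 to electrolytes. Hematology is summarised only at V4 and V6/EDV.

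- Hematology and non-electrolyte biochemistry (lipids, liver enzymes, glucose): V4, cycle 6.
- Electrolytes, including potassium: V5, cycle 9.
- Vital signs: V5, cycle 9.

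**3. The plan's own use of 45% dropout**

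The input is SAP 2.6: "Secondly, 45% of subjects are assumed to drop out of the trial". If dropouts are taken to contribute no cycles, the sample size for women aged 35 or under is

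N = 5000 / [13 × (1 − 0.45) × (1 − 0.248)] = 5000 / 5.3768 = 929.9, so 930.

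The plan states 920, which is 1.1% lower; 920 women give 920 × 5.3768 = 4947 cycles. Spreading dropout evenly over the 13 cycles gives 660, which does not match. The plan's figure thus fits 45% as the share who do not complete, which leaves 0.55 × 920 = 506 expected completers (547 of 995).

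**4. Share of the V6/EDV column from early stoppers**

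Let a be the fraction of dropouts who attend an EDV. The documents do not give it. Assume every completer has a V6 value. Then

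share = 0.45a / (0.55 + 0.45a)

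| a (assumed) | Calculation | Share |
|---|---|---|
| 0.25 | 0.1125 / 0.6625 | 17% |
| 0.50 | 0.2250 / 0.7750 | 29% |
| 0.75 | 0.3375 / 0.8875 | 38% |
| 1.00 | 0.4500 / 1.0000 | 45% |

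**5. Exposure categories**

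The cut-offs divide by 28 to give 1, 3, 6 and 9 cycles. A full course is 13 × 28 = 364 days, so the top category falls 364 − 252 = 112 days, or 4 cycles, short.

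The top row cannot stand in for completers. Of 920 women, the number reaching 252 days would be:

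- Linear dropout: 920 × (1 − 0.45 × 252/364) = 633, of whom 506 (80%) complete.
- Exponential dropout: 920 × 0.55^(252/364) = 608, of whom 506 (83%) complete.

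**The case against.** A reader might infer that safety after 13 cycles is never shown for women who had 13 cycles. The documents do not support that. Four shift tables show V6 on its own, Table 15.1.4.1.1 counts completers, bleeding is tabulated by cycle through cycle 13, and laboratory and vital-sign records are listed per subject. Nor is exposure followed only to 252 days: duration in days is summarised without a cap, and only the categories stop there.

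Other objections have weight:

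- Pooling in the vital-sign tables and the laboratory shift tables agrees with SAP 2.2.3, and for the shift tables with the protocol. Splitting these is a preference, not a correction. This stands.
- The four tables that split V6 from EDV are shift tables for assessments made only at V1a and V6/EDV. They show that the SAP can make the split, not that it intended it everywhere. This stands.
- Only the last column is affected, and potassium, weight and blood pressure are unmixed to cycle 9. This is true, but hematology, lipids and liver enzymes are unmixed only to cycle 6.
- V6/EDV is a legitimate last-visit summary, and a V6-only column describes a selected group who stayed. This is a reason to keep V6/EDV and show all three, not to omit V6.
- A cut at 364 days is not the same as 13 completed cycles. Duration is last minus first intake plus one, and a last-intake date without a day is imputed to month end (SAP 4.6). A completer whose last recorded intake is day 363 would fail the cut, and a late imputed date could pass it. This stands and shapes the fix.
- The protocol's 200-woman statement does not promise a completers-only table. This stands.

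The column layout here is read from the SAP text and table comments, since the detailed table specifications are not reproduced.

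**Conclusion.** The point holds for the laboratory change summaries. SAP 5.6.3 departs from both the protocol synopsis and SAP 2.2.3 without a stated reason, and no laboratory change summary shows V6 alone. Early stoppers would make up about 17% to 45% of the final column. That range rests on the 45% planning dropout, on an assumed EDV attendance of 25% to 100%, and on every completer having a V6 value. The direction of any distortion cannot be determined from the documents, and none has been estimated for any parameter.

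For vital signs the pooling limits interpretation but contradicts nothing. For exposure, the missing 13-cycle row is a convenience gap, since completers are counted in the disposition table. All of these are descriptive safety summaries; the Pearl Index and the sample size are untouched.

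**What to change.** 1. Reconcile SAP 5.6.3 with the protocol synopsis and SAP 2.2.3. In Tables 15.3.3.1.1 and 15.3.3.1.2, show V6 (scheduled, cycle 13) and EDV as separate columns beside V6/EDV, and name V6 as the 13-cycle laboratory change result.
2. As an improvement, make the same split in the vital-sign tables (15.3.2.1.1 to 15.3.2.1.6). The laboratory shift tables may stay pooled.
3. Add a row to Table 15.1.17.1.1 for women who completed 13 cycles, defined by completion status or cycle count and not by a strict 364-day cut, so that the target of 200 can be checked there.

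The cost is SAP wording, two extra columns per affected table and one row. No new data are needed, because trial completion is already recorded (SAP 5.1.1) and the V6/EDV split is already specified for four other tables. With about 506 expected completers among 920 women, the V6 column would be well filled.
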